4.2.2.4 Methodology – internal validation

Overall model fit will once again be examined by Cox and Snell's R². Internal validation is required to obtain an unbiased estimate of the developed model's predictive performance and, if necessary, adjust the developed model for optimism. Bootstrap resampling with 1000 replications will be used as it leads to accurate estimates of model performance [70]. Bootstrapping will also enable us to examine model consistency across bootstrap samples in terms of the selected predictors and the functional form of the continuous predictors. If necessary, we will revise our model if the original predictors or functional forms are not commonly chosen across bootstrap samples [71]. The final model will also be adjusted for optimism using uniform shrinkage [72].

4.2.3 Selection of model to be tested for external validation in Phase 3

Depending on the findings of phase 2, the model taken forward for external validation in phase 3 will either be (1) an existing model which will be updated using data from the IPD meta-analysis (as per section 4.2.1) or (2) a new model developed based on available IPD data (as per 4.2.2). However, if the updated model (4.2.1) or the new model (4.2.2) are not satisfactory due to limitations with available data, and an existing model with promising properties from previous internal and external validation studies is identified through stage 1 literature searches, this will be also evaluated in phase 3 in addition to any new model developed as part of the phase 2 work.

4.3 Phase 3: External validation of the prognostic tool

4.3.1 Design:

Prospective cohort study of individuals meeting the ARMS criteria, with 12 month follow up.

4.3.2 Aim:

To assess the external validity of the new prognostic tool

4.3.3 Hypothesis:

That the new prognostic tool will have better predictive validity for onset of psychosis in the ARMS group than the existing method of using the CAARMS.

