4.3.5 Target population

Inclusion criteria:

Individuals attending secondary care services in the NHS aged 16 to 35 who meet ARMS
criteria, as defined by the CAARMS. These validated operationalised criteria have been
published previously and consist of cut-offs regarding intensity, frequency duration of

psychotic-like experiences and functional impairment [73]. The age range is included in the ARMS criteria and reflects that most psychotic disorders have their onset in late adolescence early adulthood [74]. The ARMS criteria have not been validated in older populations [75].

- In contact with NHS Early Intervention Services or Child and Adolescent Mental Health Services
- Individuals must be able to give informed consent for the follow up subsample.

Exclusion criteria:

- History of a treated or untreated psychotic episode of one week's duration or longer;
- Previous or current treatment with antipsychotics at dose of over 5 mf of haloperidol or equivalent for over 3 weeks

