4.3.12 Analysis

Predictive validity: Effect of applying the prognostic tool versus usual practice will be assessed in the analysis. Treatments received (e.g. number of sessions of cognitive therapy) will be added as covariates in the analysis. External validation of the model will be undertaken by evaluating the discrimination and the calibration of the model developed in Phase 2 in the cohort of patients collected in Phase 3. Calibration refers to how closely the probability of the event predicted by the model agrees with the observed probability. It will be assessed graphically [60] – if predicted and observed probabilities agree over the whole range of probabilities, the plot shows a 45° line. The discriminative ability of the model will be measured with the *c* index. The *c* index is similar to the area under the receiver operating characteristic curve for logistic models and is measured on a scale ranging from 0.5 (no better than chance) to 1 (perfect prediction)[62].

Acceptability: Descriptive statistics will be used to summarise recruitment and attrition. Reasons for non-completion of any measures will be recorded and summarised.

Controlling for treatment received: Treatments received (e.g. number of sessions of cognitive therapy) will be added as covariates in the analysis.

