It is anticipated that a Markov cohort model [89] will be an appropriate vehicle to capture transition between at risk, treated health states and the longer term recovery/relapse cycle of psychosis. The model will synthesise data from several sources to estimate the probability, costs and health benefits of events/health states. These include the data collected in Phases 1-3 to estimate probability of transition between risk states, with and without the prognostic tool, the costs and health benefits of the different risk states with and without appropriate treatment, the costs and health benefits of recovery and relapse states for psychosis. Data from systematic reviews, meta-analysis and controlled trials will be preferred to data from other sources. Probabilistic sensitivity

analysis will be used to account for data uncertainty in all analyses. Structural uncertainty will be assessed in the sensitivity analyses, threshold and scenario analyses outlined above.

5. Research timetable

The overall project will be undertaken over 51 months (01/10/18 - 31/12/22).

Phase 1 (evidence synthesis) will be completed within 16 months (01/10/18 – 01/02/2020). Prior to the start of the project, we will continue to consolidate our collaborative network and invite principal investigators of relevant ARMS cohort studies to join this collaboration. Between 01/10/18 to 01/01/19 we will finalise our review protocols and literature searches to identify all relevant IPD sets. The retrieval and processing of IPD will be completed by 31/11/19. In parallel, we will conduct the systematic review of multivariable prognostic models in the ARMS group (completed by 31/12/2019) and the focused health economic review. Data-analysis will be completed in parallel with the Phase 2 analyses (01/12/19 – 31/03/20). The Phase 1 findings will be written-up for publication by the 31/06/2020. In terms of health economic analyses, development and validation of decision analytic model structure and assumptions will be completed by 31/03/20. Estimation and validation of probability, cost and health benefit variables, initial analyses and model verification will take place between 01/04/20 and 31/10/22.

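### The Phase 3 hypothesis names no CAARMS comparator that varies within the cohort, and a single cohort cannot deliver the promised effect of applying the tool versus usual practice

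*Protocol*

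**What the plan says.** Section 4.3.1 of the protocol defines Phase 3 as a "Prospective cohort study of individuals meeting the ARMS criteria, with 12 month follow up". The aim in 4.3.2 is "To assess the external validity of the new prognostic tool". The hypothesis in 4.3.3 goes further and claims "better predictive validity for onset of psychosis in the ARMS group than the existing method of using the CAARMS".

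The inclusion criteria in 4.3.5 admit "Individuals attending secondary care services in the NHS aged 16 to 35 who meet ARMS" criteria as the CAARMS defines them. Those criteria were "published previously and consist of cut-offs regarding intensity, frequency duration of" psychotic-like experiences, together with functional impairment. Under 4.3.7, a CAARMS more than 4 weeks older than the additional measures is repeated to confirm that the person is still eligible.

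The predictive validity paragraph of 4.3.12 opens with: "Effect of applying the prognostic tool versus usual practice will be assessed in the analysis". It then describes the calibration and c index of the one model from Phase 2, with treatments received added as covariates. The economic part of 4.3.12 lists among its inputs "data collected in Phases 1-3 to estimate probability of transition between risk states, with and without the prognostic tool".

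Section 4.3.6 justifies the sample size by the need for at least 100 transitions to assess calibration-in-the-large and the calibration slope. It does not mention a comparison between two predictors.

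**The concern.** A claim of superiority needs a comparator that can differ between participants. Everyone in the cohort has passed the CAARMS threshold, so entry status cannot separate those who develop psychosis from those who do not. Read that way, the only stated Phase 3 hypothesis is won almost automatically. Read any other way, the comparator is undefined. In either case, a report that the tool outperformed the CAARMS would carry little information.

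The sentence in 4.3.12 is a separate problem. An effect of applying a tool, set against usual practice, needs people or periods with and without the tool. The cohort has neither. A conclusion drawn under that sentence would have no support in the design, and adding treatments received as covariates does not create the missing contrast.

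**Working it through.** **1. The plan's own figures (4.3.6).**
- Followed up: 798 × 0.70 = 558.6 (stated 558).
- Transitions at 20%: 558 × 0.20 = 111.6 (stated 112).
- Transitions at 18%: 558 × 0.18 = 100.4 (stated 100).

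All reproduce, so the arithmetic is not at issue. The base case is n1 = 112 transitions and n0 = 558 − 112 = 446 non-transitions.

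**2. Comparator = CAARMS entry status.** The c index is the share of transition/non-transition pairs ranked correctly, with ties counting one half. A constant marker ties every pair, so c = 0.5 exactly. That is the value 4.3.12 itself describes as no better than chance.

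**3. What it takes to beat that comparator.** Under c = 0.5:

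SE = √[(n1 + n0 + 1) / (12 × n1 × n0)] = √[559 / (12 × 112 × 446)] = 0.0305

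Two-sided 5% threshold: 0.5 + 1.96 × 0.0305 = 0.56.

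A tool with a true c of only 0.60 would reach this with power of about 0.91 at 112 events, and 0.88 at the conservative 100 events.

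**4. Comparator = a graded baseline CAARMS score.** The protocol names none, so three inputs are assumed: c = 0.60 for the CAARMS score, c = 0.70 for the tool, and a correlation r between the two c estimates of 0.2 to 0.7. The Hanley-McNeil standard errors at 112/446 are s1 = 0.0310 (c = 0.60) and s2 = 0.0297 (c = 0.70).

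SE of the paired difference = √(s1² + s2² − 2·r·s1·s2)

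Gain needed for 80% power at two-sided 5% ≈ 2.8 × SE, since 1.96 + 0.84 = 2.8.

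| r (assumed) | SE of difference | Gain needed |
|---|---|---|
| 0.7 | 0.0235 | 0.066 |
| 0.5 | 0.0304 | 0.085 |
| 0.3 | 0.0359 | 0.101 |
| 0.2 | 0.0384 | 0.107 |

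For r from 0.3 to 0.7 at 112 events, power is 0.80 to 0.99 for an assumed 0.60 against 0.70, but only 0.28 to 0.56 for 0.60 against 0.65.

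**5. Tool versus usual practice.** No figure can be computed. Sections 4.3.1 and 4.3.7 describe one cohort, with no comparison group and no period before the tool. The only tool versus no-tool contrast in the protocol is the exploratory decision model in 4.3.12, which simulates it.

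**The case against.** A reader might infer that the hypothesis cannot be tested at all. The protocol does not support that. Section 4.3.3 does not say that using the CAARMS means the yes/no threshold. The criteria rest on graded dimensions, section 4.1.1 distinguishes three ARMS groups, and a baseline CAARMS is available for every participant. A severity score or intake group could therefore serve as a comparator within the cohort. This objection stands: the fault is an unspecified comparator, not an untestable question.

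It can also be said that the choice of score and difference measure belongs in a statistical analysis plan, which is not at hand. That is fair for the detail. But the hypothesis, the entry rule and the single-cohort design are all fixed in the protocol, and they do not fit together as written. No analysis plan can create a group managed without the tool.

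The effect sentence may be only a loose restatement of the hypothesis, since it sits under predictive validity and is followed by calibration and discrimination. That is plausible, and the protocol nowhere says outright that Phase 3 estimates an effect of the tool on outcome. The words still promise something the design cannot give.

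A further tempting inference is that an invalid effect estimate feeds the cost-effectiveness model. The protocol does not show this. Section 4.3.12 calls that analysis exploratory, draws on several sources, and uses threshold and scenario analyses to find how effective the tool would have to be. Only the wording about probabilities with and without the tool needs clarifying.

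**Conclusion.** The point holds for the wording of 4.3.3 and the effect sentence in 4.3.12. If the comparator is CAARMS entry status, better than CAARMS means better than chance, and an observed c of about 0.56 would establish it at the planned 112 events. That result rests only on the protocol's own numbers and the definition of the c index. The effect of applying the tool versus usual practice is not estimable from Phase 3, whatever is assumed.

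The 0.066 to 0.107 range for a graded comparator is illustrative. It depends on assumed c values of 0.60 and 0.70 and an assumed correlation from 0.7 down to 0.2, and the conclusion does not rest on it.

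This should be fixed, but it does not threaten the main deliverable. The aim in 4.3.2, objective 3b, the sample size and the analysis actually described all concern the calibration and c index of the tool, and these are unaffected.

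**What to change.** - **Section 4.3.3:** either name one prespecified comparator from the baseline CAARMS already collected (a severity score or intake group) and report the paired difference in c index with its 95% CI, or restate the hypothesis as external validation so that it matches 4.3.2.
- **Section 4.3.12, predictive validity:** delete the sentence on the effect of applying the tool, or replace it with that predictive comparison.
- **Section 4.3.12, economics:** state that the transition probabilities with and without the tool are modelled scenarios, not an effect observed in Phase 3.
- **Section 4.3.6:** if the comparison is kept, state the precision expected for the difference and the assumptions behind it.

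Net benefit of the tool is an optional addition. Setting it against treating everyone with an ARMS would need its own justification, because the protocol does not state that this is current practice.

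The cost is wording plus at most one paired analysis on data already collected; no extra participants or visits are needed. The price of naming a real comparator is that the claim becomes harder to win, and a modest gain over the CAARMS may not be distinguishable from none at this sample size.

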4.3.4 Setting

Secondary NHS services that manage ARMS individuals in the North West, North East and West Midlands, covering the NHS Trusts of Greater Manchester, Lancashire, Birmingham, Solihull, South Staffordshire, Black Country, Worcester, Warwick, Coventry, Northumberland Tyne and Wear, Tees Esk and Wear Valley and Cumbria. Additionally, we include "Forward Thinking Birmingham", a youth mental health service that provides NHS services to people aged 0-25, including ARMS patients. All services already use the CAARMS to assess for an ARMS. Clinicians at all services have received training in use of the CAARMS funded by NHS England and developed by Lead Applicant [name].

4.3.5 Target population

Inclusion criteria:

Individuals attending secondary care services in the NHS aged 16 to 35 who meet ARMS
criteria, as defined by the CAARMS. These validated operationalised criteria have been
published previously and consist of cut-offs regarding intensity, frequency duration of

psychotic-like experiences and functional impairment [73]. The age range is included in the ARMS criteria and reflects that most psychotic disorders have their onset in late adolescence early adulthood [74]. The ARMS criteria have not been validated in older populations [75].

- In contact with NHS Early Intervention Services or Child and Adolescent Mental Health Services
- Individuals must be able to give informed consent for the follow up subsample.

Exclusion criteria:

- History of a treated or untreated psychotic episode of one week's duration or longer;
- Previous or current treatment with antipsychotics at dose of over 5 mf of haloperidol or equivalent for over 3 weeks

4.3.6 Sampling

Consecutive sampling will be used.

Sample size: We aim to recruit 798 ARMS individuals over 18 months, with an anticipated attrition rate of 30% leaving a target follow-up of 558 participants at 12 months. Using an estimated 20% rate of development of psychosis ("transition rate") within 12 months we expect to see 112 cases of psychosis ("transitions"). A more conservative estimate would be 100 transitions (18% transition rate). This estimated transition rate is based on recent data of an over 25% rate in Early Intervention for Psychosis Services (EIPS) in both Manchester and Warwick. This rate, which is higher than those recently reported [76], is to be expected given the change in the way that many ARMS patients are now coming to clinical attention following implementation of the Access and Waiting Times Standard in Early Psychosis [11]. This Standard requires all individuals referred to EIPS in England to be assessed within 2 weeks. If they are found not to have a psychosis then they must be assessed for presence of an ARMS. This means that many ARMS individuals have high levels of symptoms (they were thought to actually have psychosis by referrers). This pathway is similar to the first ever ARMS service established in Melbourne by Lead Applicant [name]. This service (the PACE Clinic [36]) managed individuals who were referred to the EIPS but were found to be below threshold for psychosis. Reflecting this, the rate of development of psychosis in early studies was 35-41% within 12 months [5, 77].

Justification of Sample Size: We expect to see 100 - 112 transition events during the study. Latest research regarding sample size calculations for external validation studies suggests at least 100 events and 100 non-events to access calibration-in-the-large and calibration slope, and at least 200 events and 200 non-events to derive flexible calibration curves for logistic regression [78, 79]. This was demonstrated via assessment of multiple measures of calibration including the c-statistic, calibration-in-the-large, and calibration slope using five established simulated examples [80].

Whilst flexible calibration curves are desirable for individual risk communication, they are unrealistic in empirical medical research which must provide value for money research outputs. Prediction models that are calibrated via calibration-in-the-large and calibration slopes guarantee that clinically non-harmful decisions are made based on the model [78]. Therefore, calibration-in-the-large and calibration slope will be sufficient to determine this level of external validation of our prognostic tool. Therefore, a dataset with at least 100 transition events is required.

Feasibility of recruitment: In the 12 months from July 2016 to June 2017, our included Trusts managed 887 ARMS individuals (420 Midlands, 294 North West, 163 North East and 10 Cumbria). We will recruit for 18 months. Even after allowing for year to year fluctuations and potential for less ARMS cases we will still be able to recruit 798 ARMS individuals. Allowing for 30% attrition over 12 months results in 558 individuals retained.

4.3.7 Data Collection

All data will be collected by clinicians working in NHS clinical services or by a research assistant employed by the clinical teams to support data collection and extraction. Data will be anonymously transferred by the research assistant in the clinical team to the research database which contains a unique participant identifier.

Participants in the main prospective observational cohort will have the option to 'opt out' of their routinely collected data being used for the research study using a combined information sheet and opt out form.

5a) Main cohort

Baseline: CAARMS assessment will have been routinely completed by NHS clinicians, or a research assistant employed within the clinical team, to determine ARMS status at point of entry to their service. The Research Assistants within the clinical teams will conduct the brief set of non-invasive measures to inform the refined prognostic model. If the CAARMS assessment was done over 4 weeks before the additional measures, it will be repeated by the Research Assistant in the clinical team to ensure that the individual still meets ARMS criteria.

12 and **24** month follow up of routine data: All participants in the cohort will be followed up via the clinical notes at 12 and 24 months. The research assistant within the clinical team will use the clinical records to determine if transition to a first episode of psychosis has occurred. This will be informed by clinician's notes which may include the following:

- Standard diagnostic classification systems (DSM-III, DSM-IV, DSM-5, ICD-10, ICD-11) or commonly used ARMS assessment schedules (e.g. SIPS or CAARMS)
- Standard treatment pathway decisions by clinicians- i.e. moved to a first episode psychosis treatment pathway
- A treated or untreated psychotic episode of one week's duration or longer;
- Treatment with antipsychotics at dose of over 5 mg of haloperidol or equivalent for over 3 weeks

5b) Cohort subsample

Participants in the main cohort will be invited to opt in to an additional phase of the study, where they will meet with the research assistant employed by the clinical team at 12 months after they entered the clinical service, to repeat the CAARMS assessment and some additional measures as described below. If participants decide they would like to opt in, they will be given a leaflet explaining the study and complete a consent form before their assessment.

12 month follow up for cohort subsample: CAARMS assessment will be completed by Research Assistants at 12 month follow up for a subsample of participants (minimum of 100 participants) who consent to this part of the study at their baseline assessment with the service. The 12-month time frame has been chosen as our previous cohort studies have found that most transitions to psychosis occur during this period [5, 31]. We will also include the EQ-5D-5L [32] and a core service use form [33] adapted from previous economic evaluations in mental health. These data will be used to generate estimates to populate the decision analytic model described below.

Minimising attrition: Attrition will be minimised by offering participants reimbursement of £25 per assessment. We will ask participants for the contact details of someone (relative or friend) who might know their whereabouts if they move during the follow up period. This strategy has received ethical approval in previous studies and is effective at reducing attrition.

Additionally, we will contact participants at 6 months using a method of their choice (phone, text, email, letter etc.) to 'check in'. This will be an opportunity to check contact details are up to date and

check if the participant is still with the clinical service. We will send participants a £5 voucher to thank them for keeping in touch.

We will also apply usual good practice in trial management by continuously monitoring completion of data at all visits and identify any sites that need help in achieving and maintaining high rates of return. Weekly management supervision of Research Assistants will monitor compliance to follow-up rates and solve problems relating to attrition as they arise.

Long term follow up of routine data in future studies: Additionally, through seeking consent with subsample participants to access health records up to 5 year follow up, the long term predictive validity of the prognostic model can be assessed in the sample in future research and potentially linked to other downstream physical and mental health outcomes available via electronic record records and other routine databases. Participation in any future studies and consent to contact about future studies will be completely optional.

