4.3.9 Assessment of primary outcome

The primary outcome is development of psychosis by 12 month follow up. Psychosis onset will be assessed using the standard definition of psychosis included in the CAARMS. (This is essentially 7 days or more of full threshold psychotic symptoms occurring at least several times per week) or by clinician's notes on transition events which may include the following:

- Standard diagnostic classification systems (DSM-III, DSM-IV, DSM-5, ICD-10, ICD-11) or commonly used ARMS assessment schedules (e.g. SIPS or CAARMS)
- Standard treatment pathway decisions by clinicians- i.e. moved to a first episode psychosis treatment pathway
- A treated or untreated psychotic episode of one week's duration or longer;
- Treatment with antipsychotics at dose of over 5 mg of haloperidol or equivalent for over 3 weeks.

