Prior to the start of Phase 3, we will ensure researchers at all sites receive training in Good Clinical Practice. Each site will have a weekly team meeting and the Manchester-based project manager, who will conduct weekly telephone supervision with all RAs that will focus on recruitment, liaison with referrers, compliance to follow-ups, and scoring queries for assessment measures. Lead Applicant [name], who developed the CAARMS and associated training material, will provider regular monthly CAARMS supervision for Research Assistants and the Project manager and will be available for ad hoc scoring queries. She already provides monthly CAARMS supervision for Manchester-based clinicians and will extend this to other sites (via videoconferencing/ teleconference). These meetings will be supplemented by local supervision by site-PIs, focusing on problem solving and adherence to local policies and procedures.

8. Publication policy

In addition to the HTA report, the findings of this project will be published as series of papers in peer-reviewed journals. Group authorship on all outputs arising from the Phase 1 IPD meta-analysis will be offered to collaborators who will provide relevant IPD for the evidence synthesis conducted as part of this project.

9. Conflicts of interest

The applicants have no conflicts of interest to declare

10. Funding acknowledgement:

This project was funded by the NIHR Health Technology Assessment Programme (project number 17/31/05)

11. Department of Health disclaimer:

The views expressed are those of the authors and not necessarily those of the NHS, the NIHR or the Department of Health.

References

- 1. Global Burden of Disease Study, C., Global, regional, and national incidence, prevalence, and years lived with disability for 301 acute and chronic diseases and injuries in 188 countries, 1990-2013: a systematic analysis for the Global Burden of Disease Study 2013. Lancet, 2015. 386(9995): p. 743-800.
- 2. Häfner, H., et al., *The ABC schizophrenia study: a preliminary overview of the results.* Social Psychiatry and Psychiatric Epidemiology, 1998. 33(8): p. 380-386.
- 3. Schizophrenia Commission, *Schizophrenia The Abandoned Illness*, R. Murray, Editor 2012.
- 4. [name], A., et al., *Monitoring and care of young people at incipient risk of psychosis.* Schizophrenia Bulletin, 1996. 22(2): p. 283-303.

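### One role, the research assistant in the clinical team, takes the baseline prognostic measures and decides 12-month transition, and nothing masks the outcome rater

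*Protocol*

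**What the plan says.** Baseline, section 4.3.7 (main cohort): "The Research Assistants within the clinical teams will conduct the brief set of non-invasive measures to inform the refined prognostic model". If the routine CAARMS is more than four weeks old, "it will be repeated by the Research Assistant in the clinical team to ensure that the individual still meets ARMS criteria".

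Outcome, main cohort, same section, covering both routine follow-ups (month 12 and month 24), is described thus: "The research assistant within the clinical team will use the clinical records to determine if transition to a first episode of psychosis has occurred".

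Outcome, subsample, section 4.3.7: "CAARMS assessment will be completed by Research Assistants at 12 month follow up for a subsample of participants (minimum of 100 participants").

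Outcome definition, section 4.3.9: psychosis by the CAARMS threshold, "or by clinician's notes on transition events which may include the following". Four kinds of evidence follow: a diagnosis or assessment schedule, a pathway move, an episode lasting a week or more, and antipsychotic treatment above a stated dose and duration. The pathway item reads "Standard treatment pathway decisions by clinicians- i.e. moved to a first episode psychosis treatment pathway".

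Oversight, section 7: monthly CAARMS supervision, weekly supervision that covers "compliance to follow-ups, and scoring queries for assessment measures", and a monitoring committee that looks at data quality. The protocol does not mention masking of the outcome rater, a different rater, adjudication, or a comparison of notes with the repeat CAARMS.

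**The concern.** In an external validation study, outcomes should be rated without knowledge of the predictors. Here predictor measurement and outcome determination sit with one role in one team, and the outcome is not a hard endpoint. The notes may contain any of several kinds of evidence, with no ranking or decision rule among them. The CAARMS rule depends on symptom threshold, frequency and duration. Section 4.3.6 adds that many of these patients were thought by their referrers to be psychotic already, so borderline records are plausible.

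If a rater who knows the baseline picture is readier to call transition in a high-risk person, or slower to call it in a low-risk one, the misclassification is tied to the predictor. Error of that kind pushes the c index and calibration slope up, whereas error unrelated to risk pulls them down. Discrimination and calibration are what Phase 3 exists to estimate (sections 4.3.6 and 4.3.12). Once outcomes have been labelled this way, the analysis cannot readily undo it. Section 6 intends the resulting calculator for immediate use.

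**Working it through.** **The plan's own figures (section 4.3.6).** Followed up: 798 × (1 − 0.30) = 558.6, stated as 558. Transitions: 558 × 0.20 = 111.6, stated as 112; 558 × 0.18 = 100.4, stated as 100. All reproduce and none is disputed. Non-events: 558 − 112 = 446.

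**Precision of c (Hanley–McNeil), c = 0.65, 112 events, 446 non-events.**
- Q1 = c/(2 − c) = 0.65/1.35 = 0.4815
- Q2 = 2c²/(1 + c) = 0.845/1.65 = 0.5121
- Variance = [c(1 − c) + 111(Q1 − c²) + 445(Q2 − c²)]/(112 × 446) = (0.2275 + 6.55 + 39.88)/49,952 = 0.000934
- SE = 0.031 (0.032 with 100 events and 458 non-events)

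**Illustration of bias.** The documents give no error rates, so every rate below is an assumption. Simulated cohorts of 400,000 had a true c of 0.65, a true slope of 1 and a 20% transition rate. Outcomes were then relabelled with error, and c and the recalibration slope recomputed. FP is the share of non-transitions called transition; FN is the share of transitions missed.

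| Assumed error | Observed c | Change from 0.65 | Slope |
|---|---|---|---|
| Unrelated to risk: FP 3%, FN 15% | 0.625 | −0.025 | 0.82 |
| Moderate lean: FP 5% top third, 2% elsewhere; FN 20% bottom third, 10% elsewhere | 0.653 | +0.003 | 1.00 |
| Stronger lean: FP 8% and 2%; FN 30% and 10% | 0.673 | +0.023 | 1.14 |
| Outer thirds only: FP 2% top, FN 5% bottom | 0.662 | +0.012 | 1.07 |
| Outer thirds only: FP 5%, FN 10% | 0.677 | +0.027 | 1.18 |
| Outer thirds only: FP 10%, FN 20% | 0.701 | +0.051 | 1.35 |

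In standard errors, the two leans with background error give 0.003/0.031 = 0.1 and 0.023/0.031 = 0.7. The harshest outer-thirds setting gives 0.051/0.031 = 1.6. At that setting a true c of 0.60 appears as 0.66 (slope 1.55) and 0.75 as 0.78 (slope 1.18). The observed transition rate stays between 0.195 and 0.215 throughout, so calibration-in-the-large would hardly reveal the problem.

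**The case against.** The strongest reply is that much of the rating is extraction rather than opinion. A recorded diagnosis, a pathway move and a treatment record are decisions that clinicians have already made, and two of the listed items carry explicit duration or dose thresholds. Supervision and data-quality monitoring are in place. This limits the room for judgement but does not remove it: the list is open-ended, the CAARMS needs scoring, and supervision is not masking.

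Four stronger readings are tempting, and the documents do not support them.

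- **One person does both tasks for each participant.** The protocol names the same role, not the same individual, and the baseline CAARMS may be done by a clinician. The fair statement is that nothing separates the tasks.
- **The tool's score is shown to raters or treating teams.** No section says so. The calculator in section 6 is an output of the project, and section 4.3.8 leaves the tool's variables open until Phases 1 and 2 finish. The protocol simply does not say who may see a predicted risk.
- **Lack of masking adds 0.03 to 0.05 to c in the moderate scenarios.** That figure comes from comparison with the risk-independent row, which has a different error mix and itself lies below the truth. Against the true 0.65, those two scenarios add 0.00 to 0.02.
- **A higher slope flatters the tool.** The ideal slope is 1, so 1.14 is poorer apparent calibration. It would flatter the tool only if the true slope were below 1.

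It is also fair that masking the research assistant leaves the treating clinicians unmasked. They write the notes and decide pathways, and they may know the baseline CAARMS.

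**Conclusion.** The concern stands as a design weakness. Sections 4.3.7 and 4.3.9 place predictor measurement and a partly judgement-based primary outcome with the same role and do not mask the outcome rater. Outcome errors may therefore follow baseline risk and bias the c index and calibration slope. Whether they will, and by how much, cannot be known from the documents.

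Under assumed error rates, inflation over a true c of 0.65 runs from about 0.00 to 0.02 in the moderate scenarios to about 0.05 in the harshest one, against a standard error of about 0.03. The slope could move above 1. The upward direction depends on the assumption that errors lean with baseline risk. No sample-size figure changes. Who rates the primary outcome, and what that person knows, is a data-collection choice made in the protocol rather than a detail left to the analysis plan.

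**What to change.** State in sections 4.3.7 and 4.3.9 that:

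- (a) the 12- and 24-month outcome is coded by a research assistant who did not take that participant's baseline measures, where the team has more than one; otherwise it is coded from post-baseline records without opening the baseline measures;
- (b) the tool's predicted risk is calculated centrally and not released to research assistants or treating teams until that participant's 12-month outcome is locked;
- (c) the subsample's 12-month CAARMS is rated without the baseline CAARMS sheet, and agreement between notes-based and CAARMS-based transition is reported in that subsample.

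The cost is protocol wording and a little research-assistant scheduling. No note text needs to move between sites, so the anonymised transfer arrangement in section 4.3.7 is unchanged. A lone research assistant may still remember a participant, and clinicians who know the baseline CAARMS still write the notes and make the pathway decisions. Only part of the bias is removed, and the protocol and report should state this as a limitation.
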